5.1 INTERVENTION GROUPS

This study will have an active control group (Group A) and three intervention groups;

Group A: will receive hand therapy

Group B: will receive a thermoplastic wrist splint + hand therapy

Group C: will receive a corticosteroid injection to the TFCC + hand therapy

Group D: will receive a thermoplastic wrist splint + corticosteroid injection to the TFCC + hand therapy

Participants will be randomly allocated to a treatment group following informed consent and a baseline research assessment.

5.2 STUDY LOCATION

This investigation will be conducted at the Brisbane Hand and Upper Limb Research Institute at Brisbane Private Hospital, Brisbane, Australia. It is anticipated that the majority of the study participants will be recruited by surgeons with private consulting suites at the Brisbane Hand and Upper Limb Clinic.

5.3 STUDY DURATION

It is expected that participant recruitment will be carried out over a 24 months period, with data collection for the primary end-point anticipated to be finalised no later than 28 months from commencement. Data collection will continue for the secondary end-point, until the remaining participants are up to 24 months post baseline.

6 STUDY POPULATION

Adults presenting with a TFCC tear, no greater than 12 months from primary injury will be invited to participate in the research study. As per standard care, clinical presentation of TFCC localised ulnar-sided wrist pain in addition to radiological confirmation of tear, will be considered by the treating surgeon to determine eligibility and suitability for conservative management (*Screening and Recruitment, 8.1.1*).

6.1 ELIGIBILITY CRITERIA

6.1.1 Inclusion Criteria

Participants will be eligible for inclusion in the study if they:

1. Aged 18 years and over;
2. Have a clinical diagnosis of TFCC localised, ulnar-sided wrist pain
3. Are ≤ 12 months post initial injury;
4. Have MRI confirmation of isolated TFCC tear;

6.1.2 Exclusion Criteria

Participants will be excluded from the study if they present with:

1. Frank instability of the distal radioulnar joint (DRUJ);
2. Arthritis of the distal radioulnar joint (DRUJ);

3. Concomitant injury (e.g. scaphoid fracture) in addition to TFCC tear;
4. Splint immobilisation or steroid injection within the last 3 months, to treat current injury;
5. Pregnancy due to risks associated with the corticosteroid injections;
6. Known allergies or adverse reactions to hydrocortisone and local anaesthetic (HCLA) injections;
7. Medical dependency that may interfere with ability to complete assessments or compliance;

6.2 RISKS TO PARTICIPANTS

All treatments offered in this trial are available to patients outside of study participation. No substantial evidence exists to suggest if any of the treatments offered as part of this trial are more or less effective than other treatments available. Participants who experience no improvement in their symptoms during the study may discuss study withdrawal with their study surgeon or other health care provider to seek further treatment. As none of the study interventions differ to those that would be recommended to eligible patients as treatment options, there are no perceivable study-specific health risks to participants.

Health risks associated with the treatments offered in this study include adverse reactions to the therapy exercise, thermoplastic splint or cortisone injection. Potential risks involved with injection of Marcain and or Celestone Chronodose as with any injection include infection, bruising or bleeding or a reaction to the medication. Adverse reactions to Celestone Chronodose may include fluid and electrolyte disturbances, musculoskeletal, gastrointestinal, dermatologic, neurologic, endocrine, ophthalmic, metabolic and psychiatric issues. Adverse reaction to Marcain may be of a cardiovascular, haemodynamic, neurologic or allergic nature. Although the mentioned reactions have been documented, the likelihood of occurrence is extremely rare. Any adverse reaction from the use of the thermoplastic wrist splint, including allergic contact dermatitis (redness, itching, skin eruptions, raised temperature, swelling); miliaria rubra/prickly heat (small red elevated inflammatory papules with tingling/burning sensation); pressure or friction related complications and skin maceration from retained moisture caused by sweating or getting the splint wet and not drying properly.

Risks specific to study participation include risks relating to the collection and storage of personal data for data analysis (*Data storage, Management and Confidentiality, 9.2*).

7 STUDY OUTCOMES

Patient-reported pain and function questionnaires will be administered at baseline, 6 and 12 weeks; and 6, 12 and 24 months post baseline. Compliance and adverse events will be recorded at all post-intervention intervals, including 2 weeks after treatment initiation.

7.1 PRIMARY OUTCOME

7.1.1 Patient Rated Wrist and Hand Evaluation (PRWHE)

The Patient Rated Wrist and Hand Evaluation (PRWHE) is a patient-reported questionnaire, comprised of pain and function elements specific to wrist conditions. The 15-item questionnaire consists of two subscales designed to measure wrist pain and difficulty in activities of daily living (ADL), to give an overall score of wrist disability. It is one of the most widely used and validated instruments specific for this population.

Patients are asked to rate their pain on four items from 0 (no pain) to 10 (worst pain) and function on 10 items from 0 (no difficulty) to 10 (unable to do), including four broad ADL questions. Questions are specific to the affected wrist and can be used to calculate a total PRWHE score, in which pain and function are equally weighted. The PRWHE has been used to assess wrist-related pain and disability in various populations and its reliability, validity, and responsiveness have been extensively researched and publicized (MacDermid, Wessel, Humphrey, Ross, & Roth, 2007). A change of 14 points will be considered the minimum change to detect a difference with clinical relevance for the population.

7.2 SECONDARY OUTCOMES

7.2.1 Global Rating of Change (GRC)

The Global Rating of Change (GRC) scale provides a tool for measuring self-perceived change in health status in a quick and uncomplicated way (Kamper, Maher, & Mackay, 2009). It quantifies the extent to which the patient discerns their own improvement or deterioration over time on a 15-point scale, where 0 is no change. The GRC will be used in this study to measure change in symptoms and function between baseline and post-intervention assessment intervals. The instrument has the advantages of clinical relevance, adequate re-productibility, and sensitivity to change and is intuitively easy to understand by the patient and the person administering. Test-retest reliability is high (ICC 0.9) and face validity is supported by strong association between GRC and patient ratings of the importance of change (Pearson's $r = 0.90$) (Kamper et al., 2009). A change in symptoms or function of at least 5 points will be used to indicate a significant clinical change, perceivable to the patient.

7.2.2 Disabilities of the Arm, Shoulder and Hand, Short Form (QuickDASH)

The QuickDASH is a shortened version of the Disabilities of the Arm, Shoulder and Hand (DASH) Outcome Measure, and scoring is highly correlated to the DASH score. Both the DASH and the QuickDASH Outcome measure are valid, reliable and responsive and can be used for clinical and research purposes relating to upper limb disability (MacDermid et al., 2007; Mintken, Glynn, &

Cleland, 2009). The QuickDASH uses 11 items to measure physical function and symptoms in people with disorders of the upper limb, but questions are not specific to the affected joint. The survey is intended to be answered irrespective of the arm used to complete the activity in order to accurately capture limitations experienced whilst acknowledging adaptations made to perform activities. The QuickDASH also has two optional modules intended to measure symptoms and function in athletes, performing artists and other workers whose jobs require a high degree of physical performance.

7.2.3 Pain and Satisfaction Visual Analogue Scale (VAS)

A five-question visual analogue scale (VAS) will be used to assess wrist pain and satisfaction. These patient-reported scales are a commonly used tool for measuring pain intensity in clinical and research setting, with extensive evidence to support their validity and reliability (Ferreira-Valente, Pais-Ribeiro, & P Jensen, 2011; Hawker GA., Mian S, Kendzerska T, & French M, 2011; Price, A. McGrath, Rafii, & Buckingham, 1983). The form instructs participants to indicate their response on the 100 mm line, which is anchored at both ends with word descriptors. A score out of 100 is taken as a measurement from left (0) to the point where the patient has marked on the line.

7.2.4 Quality of Life EUROQOL (EQ-5D-5L)

The EQ-5D-5L is a generic health-related quality of life instrument completed by the patient. The instrument contains 5 multiple choice questions in the domains of mobility, personal care, usual activities, pain/discomfort and anxiety/depression. Each domain is categorised in three degrees of increasing severity or difficulty. The EQ-5D-5L has a supplementary multi-attribute score, reported on a continuous vertical VAS, ranging from 0 (worst imaginable health) to 100 (best imaginable health). This secondary outcome measure will be utilised to examine potential impacts on quality of life throughout study participation.

7.2.5 Grip and Pinch Strength

Maximal isometric grip strength will be assessed using a calibrated hydraulic Jamar™ dynamometer. Three measurements for both the hands will be recorded and an average of the three measurements will be used in the data analysis (Mathiowetz, 1990). The measurements will be performed from a seated position, alternating between left and right hands to avoid fatigue. Maximal lateral and two-point (index and thumb) pinch strength will be measured using a calibrated hydraulic Saehan™ pinch gauge. These assessments are frequently and reliably used as a measure of hand function (Mathiowetz, Weber, Volland, & Kashman, 1984) and is routinely performed as part of a patient's standard care.

7.2.6 Adverse Events

Any adverse events occurring during the trial will be closely monitored and followed up until the complete resolution of symptoms. This will include all reactions listed for the cortisone injection and any reactions to the thermoplastic splint. These will be checked at each assessment stage and recorded on the adverse events / complication forms. Adverse events may include:

1. Any adverse reaction from the intra-articular corticosteroid injection, including but not limited to those provided in the product information brochure;
2. Any adverse reaction to use of the thermoplastic wrist splint
3. Wrist instability
4. Reinjury of affected wrist
5. Other (including Chronic Regional Pain Syndrome, or hypersensitivity)

Other changes in symptoms and function noted by participants will be noted at each interval in the event that the change noted progresses to an adverse event or complication.

8 STUDY PROCEDURES

8.1 PARTICIPANT RECRUITMENT, ENROLMENT AND RETENTION

8.1.1 Screening and Recruitment

The study population will primarily be recruited from the private consulting practices of orthopaedic surgeons at the Brisbane Hand and Upper Limb Clinic at the Brisbane Private Hospital. In addition, local general practitioners will be invited to refer patients to be assessed by an orthopaedic upper limb specialist, to be considered for potential research participation.

8.1.1.1 Orthopaedic Surgeon Referral

Surgeons involved in the study will identify eligible study participants at the time of presentation to clinical appointments, based on the inclusion and exclusion criteria (*Eligibility Criteria, 6.1*). Patients with injuries deemed suitable for randomised conservative management by the treating surgeon, will be informed of the study. If the participant is interested in participation or would like more information, they will be referred to the Brisbane Hand & Upper Limb Research Institute. At the time of referral to the Brisbane Hand & Upper Limb Research Institute, the surgeon will complete a research referral indicating the participant's eligibility for study participation (Appendix 14.1). A research assistant will explain in detail the procedures, risks and benefits associated with the study and provide the Participant Information and Consent Form (PICF) for the participant to consider.

8.1.1.2 General Practitioner Referral

General Practitioners (GPs) are often the first point of contact for patients with acute or recalcitrant, ulnar sided wrist pain. GPs who frequently refer patients to surgeons at the Brisbane

Hand & Upper Limb Clinic will be notified of the study and provided with information regarding participant eligibility and study procedures. If a GP identifies a potentially eligible patient who is interested in research participation, they will provide the patient with contact details for the Brisbane Hand & Upper Limb Research Institute (BHULRI) for more information. If, after speaking to a research member, the participant decides they would like to be considered for trial participation, their GP will write a referral for an appointment with a participating orthopaedic surgeon at the Brisbane Hand & Upper Limb Clinic.

If deemed suitable for randomised conservative management and eligible for study participation, the patient will be referred to research as described above (*Orthopaedic Surgeon Referral, 8.1.1.1*).

8.1.2 Consent and Enrolment

Patients will be screened for eligibility and suitability by the referring surgeon. Consent procedures will be carried out by research assistants in line with the NHMRC National Statement on Ethical Conduct in Human Research (2007). After review of the Participant Information Consent Form (PICF) and acknowledging that they have understood the proposed research and the implications of participation, patients who voluntarily elect to participate will be asked to sign the consent form (Appendix 14.2). Once a participant has consented and completed their pre-treatment assessment, they will be randomised and allocated to an intervention group.

8.1.3 Participant Withdrawal and Attrition

8.1.3.1 *Withdrawal Prior to Treatment*

Individuals who express reluctance to receiving any of the study treatments prior to consent will be discouraged to volunteer for study participation. If a patient has consented to study participation but does not wish to follow through with their randomised treatment allocation, they will be given the option to withdraw from the study. Participants who, after receiving cortisone, splinting or therapy treatment, have not benefitted from the randomly allocated intervention may wish discuss alternatives with their treating health provider. Any additional treatment received will conclude research participation. See Section 4.8.3 for more information on participant attrition.

8.1.3.2 *Elective Withdrawal After Treatment*

Any participant who wishes to withdraw during the study of his/her own accord and for whatever reason is entitled to do so without obligation and prejudice. In the event of this occurring, the participant will be asked to sign a study withdrawal form.

Participants who, after receiving cortisone, splinting or therapy treatment, have not benefitted from the course of conservative treatment may wish to discuss alternatives with their treating

health provider. If the participant chooses to undergo additional interventions, remedies or treatment external to the study within the initial 12-week primary or 24-month secondary study end point, their active research participation will be ceased. The participant will be invited to complete a final assessment prior to receiving further treatment if possible, at which point the type of treatment planned (e.g. surgical TFCC repair) will be recorded. If the participant is agreeable, the research team will follow up (via phone or email) with inactive participants 6 months after their active research participation has concluded, to confirm details of injury resolution. Attrition rate and wrist outcomes of participants who have received treatment outside of the study protocol will be reported in the final publication.

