3.2.2 Secondary Objectives

To determine the prevalence and factors associated with triangular fibrocartilage complex tears not benefitting from a course of conservative treatment.

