8.2 RANDOMISATION

Block randomisation will be performed to achieve balance in the allocation of participants to the different treatment arms throughout the course of the recruitment period. Fifteen blocks will be generated, with three multiples of each treatment arm per block. As a result, for every 12 randomly assigned treatment allocations, each intervention arm will have a comparable number of participants.

The randomisation sequence will be concealed in sequentially numbered sealed, opaque envelopes. The randomisation procedure will be administered by a research assistant who will not be blind to allocation for the duration of the study. They will open an envelope and reveal the allocation to the patient. As all treatment groups involve a hand therapy session, all participants will be provided with a referral for hand therapy by their referring surgeon when enrolled in the study. A dual randomisation procedure will be implemented, with one envelope opened at baseline and the other at the 6 week interval. At the baseline appointment, the assessor will open an envelope to reveal whether the participant will be receiving a splint.

A second randomisation will occur at 6 weeks to reveal whether the participant is to have a cortisone injection. Each envelope will contain a sheet of paper with the intervention group, as listed below.

Group A Hand Therapy (HT)	Group B HT + Splint	Group C HT + Cortisone	Group D HT + Splint + Cortisone
-------------------------------------	-------------------------------	----------------------------------	---

If randomly allocated into Group C or Group D, the participant's study surgeon will issue a referral for a cortisone injection to be administered at Brisbane Private Imaging, 6 weeks after the baseline appointment. The treating surgeon will not be blind to allocation to maintain standard medical care.

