8.5.1 Primary End-point

Participants will be assessed by their referring surgeon and have outcomes measured by a research assistant at 12 weeks to assess effectiveness of the randomised conservative treatment for treating the injury. Patients who demonstrate no benefit from conservative management, or an aggravation in symptoms may be considered for further conservative treatment or surgical intervention at the surgeon's discretion. Any further treatment received will result in the conclusion of the participant's ongoing study involvement. Assessments will be made at 2 and 6 weeks to monitor compliance to the treatment allocated, complications/adverse events and an interim assessment of treatment outcomes (6 weeks only).

Data Collection Interval	Range	Review Method
Pre-intervention/baseline	≤ 12 months post initial injury	In person at the clinic Surgeon + Researcher + Hand Therapist
2 weeks Compliance & complications	2 weeks +/- 5 days	In person at the clinic Researcher + Hand Therapist
6 weeks Interim Assessment	6 weeks +/- 10 days	In person at the clinic Researcher + Hand Therapist + Surgeon

12 weeks Primary End-Point	2 – 4 months	In person at the clinic Surgeon + Researcher
-------------------------------	--------------	---

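### Taking further treatment ends PRWHE follow-up, so scores go missing in relation to outcome, mainly at 6 to 24 months

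*Protocol*

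**What the plan says.** The rule appears three times in the protocol. Section 8.1.3.1 states "Any additional treatment received will conclude research participation". Section 8.1.3.2 covers treatment outside the study at any time up to the 12-week or 24-month end point and says that "their active research participation will be ceased". Section 8.5.1 adds "Any further treatment received will result in the conclusion of the participant's ongoing study involvement".

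The protocol also says who is likely to take this step. Section 6.2: "Participants who experience no improvement in their symptoms during the study may discuss study withdrawal". Section 8.5.1: "Patients who demonstrate no benefit from conservative management, or an aggravation in symptoms may be considered for further conservative treatment or surgical intervention". Section 8.1.3 likewise describes people who have not benefitted.

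A person who has consented but "does not wish to follow through with their randomised treatment allocation, they will be given the option to withdraw from the study" (section 8.1.3.1). No route is described for staying in follow-up without the allocated treatment. Allocation is open. Section 8.2 says of the research assistant: "They will open an envelope and reveal the allocation to the patient". The injection allocation is revealed at week 6.

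Section 8.1.3.2 limits the loss in four ways: a final assessment before the other treatment where possible, a record of the treatment planned, one phone or email contact 6 months later if the participant agrees, and publication of attrition and of these participants' wrist outcomes. The secondary objective (section 3.2.2) is "To determine the prevalence and factors associated with triangular fibrocartilage complex tears not benefitting from a course of conservative treatment".

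**The concern.** The rule makes outcome collection depend on staying with the allocated treatment alone. Those who do badly are the ones most likely to seek something else, and once they do, no scheduled PRWHE is planned for them. If one arm works less well, more of its participants leave, and those who remain look better than the arm as randomised. Because allocation is known, willingness to leave can also differ by arm for reasons other than outcome. Being asked at week 6 to have an injection that one does not want is an added reason to leave in Groups C and D.

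Two things are at stake. The 6-, 12- and 24-month comparisons would describe mainly people who never needed anything more. The secondary objective concerns the very people whose scheduled follow-up stops. A later SAP can define analysis sets and missing-data methods, but it cannot recover scores that the protocol stopped collecting.

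**Working it through.** **1. The plan's own figures (section 9.1).** Inputs: f = 0.29, α = 0.05, four groups, numerator df 3. With λ = f²N and denominator df N − 4, the smallest N with power of at least 0.80 is 134: λ = 0.29² × 134 = 11.2694, critical F = 2.6743, power 0.8013. Allowing for 25% attrition, 134 / 0.75 = 178.7, so 179, rounded to 180. These reproduce exactly. The 25% comes from historical clinic retention. It protects power but does nothing about who is lost.

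**2. Which visits are exposed.** Section 8.5.1 has outcomes measured at the 12-week visit, where non-responders may be considered for other treatment. Someone who first takes that step after the visit keeps the primary score and loses the 6-, 12- and 24-month scores. Someone who takes it before the visit loses the 12-week score too. Section 8.1.3.2 foresees exits within 12 weeks but gives no rate.

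**3. Illustration: same leaving rule in both arms.** None of these inputs is in the documents except the 14-point threshold (sections 7.1.1 and 9.1). Assume improvements are normal with means 20 and 34 (true difference 14) and SD 22. A fraction q of those improving by less than 14 points leaves without a score; nobody else leaves. With a = (14 − μ)/σ and p = Φ(a):

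- mean of those below 14: μ − σφ(a)/p
- mean of those at or above 14: μ + σφ(a)/(1 − p)
- observed mean: [p(1 − q) × lower mean + (1 − p) × upper mean] / [p(1 − q) + (1 − p)]

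For μ = 20: a = −0.273, p = 0.393, lower mean −1.54, upper mean 33.92. For μ = 34: a = −0.909, p = 0.182, lower mean 2.04, upper mean 41.09.

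| q | Missing, worse arm | Missing, better arm | Observed means | Observed difference | Non-benefit among those scored (true 39% and 18%) |
|---|---|---|---|---|---|
| 10% | 3.9% | 1.8% | 20.9, 34.6 | 13.7 | 37%, 17% |
| 20% | 7.9% | 3.6% | 21.8, 35.2 | 13.4 | 34%, 15% |
| 50% | 19.6% | 9.1% | 25.3, 37.2 | 11.9 | 24%, 10% |
| 80% | 31.4% | 14.5% | 29.9, 39.4 | 9.6 | 11%, 4% |

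The assumed SD matters little. An f of 0.29 with a 14-point difference implies an SD from 14 × √(1/8) / 0.29 = 17.1 (two extreme arms differ, the other two midway) to 7 / 0.29 = 24.1 (two arms against two). Over that range the observed difference is 13.7 at q = 10%, 13.3 to 13.4 at 20%, 11.9 to 12.0 at 50% and 9.8 to 9.5 at 80%.

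**4. Illustration: leaving differs by arm, with no true effect.** Assume mean improvement 20 in every arm, SD 20.9, and 5% of benefiters leaving. If 25% of non-benefiters leave Group A and 10% leave Group D, Group A looks 1.4 points better than Group D. At 50% against 10% it looks 4.2 points better (3.3 to 5.0 over the SD range). With 50% in Group A and 10% in the other three, 10,000 simulated trials of 45 per arm rejected on the four-group F test in about 13% instead of 5%.

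Steps 3 and 4 compare raw means of those with a score; they are not predictions for this trial.

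**The case against.** The strongest reply is that the 12-week result may be little affected. Many non-responders will be identified at the 12-week visit itself, after their primary score is taken. A 6-week PRWHE is collected, and section 9.3 plans linear mixed models; if leaving is explained by recorded earlier scores, such a model can correct much of the bias. With 10 to 20% of non-benefiters leaving, the illustrated shift is only 0.3 to 0.6 points. All of this stands for 12 weeks. It does not stand for 6 to 24 months, where someone who moves to other treatment has no later scheduled score and the model must extrapolate from what came before.

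Four stronger readings are tempting, but the protocol does not support them.

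- *That those who decline their allocation must leave.* They are offered withdrawal, not required to take it. The gap is that no way of staying is described.
- *That recovered participants can leave only from the injection arms.* Section 8.1.3.2 lets anyone withdraw for any reason. Refusing the injection is an extra reason in Groups C and D, no more. The 57% complete resolution cited in section 2.1 cannot size this effect: it concerns radiologically unconfirmed injury after immobilisation, whereas this trial requires MRI confirmation and Groups A and C have no splint.
- *That every treatment failure loses the 12-week score.* Only those treated elsewhere before that visit do.
- *That the secondary objective is defeated.* Recorded progression to other treatment is itself evidence of non-benefit, and candidate factors are collected at baseline. The objective is weakened, because the planned final assessment is optional and untimed.

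**Conclusion.** The point holds. As written, the protocol stops scheduled PRWHE collection in people selected largely by lack of benefit, in an open-label trial, and none of its mitigations secures a scheduled score. The exposure is greatest for the 6-, 12- and 24-month results and the objective on non-benefit, and narrower at 12 weeks.

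The size cannot be stated from the document. Section 2.1 cites a retrospective review in which 15% went on to surgery and 37% were unchanged or worse on PRWHE; this suggests the group need not be small, but gives no rate by arm or within 12 weeks. Under the assumptions shown, bias against a 14-point difference runs from 0.3 points (10% of non-benefiters leaving) to 4.4 points (80% leaving). A reader might infer that the primary result is certainly distorted. The figures do not show that. They show an avoidable risk that is cheap to remove now and that later analysis cannot fully repair.

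**What to change.** In sections 8.1.3 and 8.5.1, separate stopping or declining study treatment from withdrawing consent to data collection. Replace the rule with wording such as:

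> Participants who decline their allocation or receive additional treatment stay in follow-up unless they withdraw consent to data collection. PRWHE and the secondary questionnaires are collected at 12 weeks and at 6, 12 and 24 months, by digital survey if not in person. The additional treatment and its date are recorded. Participants are compared as randomised.

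Clinical care is untouched. The recruitment target also stands: at the planned 25% loss, 180 × 0.75 = 135 remain (power 0.805).

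The cost is protocol and consent wording, plus a remote survey option at 12 weeks, which section 8.5.1 now lists as in person only. Emailed surveys already exist for the later visits (section 8.5.2). The downside is that later estimates then include the effect of any additional treatment. Keeping the pre-treatment final assessment allows a sensitivity analysis that addresses this.
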